APPENDIX 4.**SUBJECTIVE GLOBAL ASSESSMENT (SGA) TEST**

Anexo 2 299

VALORACIÓN GLOBAL SUBJETIVA GENERADA POR EL PACIENTE

Por favor, conteste al siguiente formulario escribiendo los datos que se le piden o señalando la opción correcta, cuando se le ofrecen varias

Nombre y Apellidos _____	Edad _____ años Fecha / /
PESO actual _____ kg Peso hace 3 meses _____ kg	DIFICULTADES PARA ALIMENTARSE: Sí No Si la respuesta era Sí, señale cual / cuales de los siguientes problemas presenta: falta de apetito ganas de vomitar vómitos estreñimiento diarrea olores desagradables los alimentos no tienen sabor sabores desagradables me siento lleno enseguida dificultad para tragar problemas dentales dolor. ¿Dónde? _____ depresión problemas económicos
ALIMENTACIÓN respecto hace 1 mes: como más como igual como menos Tipo de alimentos: dieta normal pocos sólidos sólo líquidos sólo preparados nutricionales muy poco	
ACTIVIDAD COTIDIANA en el último mes: normal menor de lo habitual sin ganas de nada paso más de la mitad del día en cama o sentado	
Muchas gracias. A partir de aquí, lo completará su Médico	
ENFERMEDADES: _____ _____	EXPLORACIÓN FÍSICA: Pérdida de tejido adiposo: Sí. Grado _____ No Pérdida de masa muscular: Sí. Grado _____ No Edemas y/o ascitis: Sí. Grado _____ No Úlceras por presión: Sí No Fiebre: Sí No
TRATAMIENTO ONCOLÓGICO: _____ _____	
OTROS TRATAMIENTOS: _____ _____	
ALBÚMINA antes de tratamiento oncológico: _____ g/dl	
PREALBÚMINA tras el tratamiento oncológico: _____ mg/dl	

VALORACIÓN GLOBAL, teniendo en cuenta el formulario, señale lo que corresponda a cada dato clínico para realizar la evaluación final:

DATO CLÍNICO	A	B	C
Pérdida de peso	<5%	5-10%	>10%
Alimentación	Normal	deterioro leve-moderado	deterioro grave
Impedimentos para ingesta	NO	leves-moderados	graves
Deterioro de actividad	NO	leve-moderado	grave
Edad	65	>65	>65
Úlceras por presión	NO	NO	SI
Fiebre / corticoides	NO	leve / moderada	elevada
Tto. antineoplásico	bajo riesgo	medio riesgo	alto riesgo
Pérdida adiposa	NO	leve / moderada	elevada
Pérdida muscular	NO	leve / moderada	elevada
Edemas / ascitis	NO	leve / moderados	importantes
Albúmina (previa al tto)	>3,5	3'0-3,5	<3,0
Prealbúmina (tras tto)	>18	15-18	<15

VALORACIÓN GLOBAL,

- A: buen estado nutricional
- B: malnutrición moderada o riesgo de malnutrición
- C: malnutrición grave

**VALORACIÓN GLOBAL SUBJETIVA
GENERADA POR EL PACIENTE (VGS-GP)**

HISTORIAL

Identificación del paciente:

A RELLENAR EXCLUSIVAMENTE POR EL PACIENTE

1. Peso:

Consideraciones sobre mi peso actual y sobre la evolución de mi peso en las últimas semanas:

En la actualidad peso alrededor de _____ kilos

Mido aproximadamente _____ cm

Hace un mes pesaba alrededor de _____ kilos

Hace seis meses pesaba alrededor de _____ kilos

Durante las dos últimas semanas mi peso:

- ha disminuido
- no ha cambiado
- ha aumentado

(ver Tabla 1 en la hoja de instrucciones)

2. Ingesta: en comparación con mi estado habitual, calificaria a mi alimentación durante el último mes de:

sin cambios

mayor de lo habitual

menor de lo habitual

Ahora como:

alimentos normales pero en menor cantidad de lo habitual

pocos alimentos sólidos

solamente líquidos

solamente suplementos nutricionales

muy poco

solamente alimentación por sonda o intravenosa

(consignar como marcador final la condición de más alta puntuación)

3. Síntomas: he tenido los siguientes problemas que me han impedido comer lo suficiente durante las últimas dos semanas (marcar según corresponda):

- no tengo problemas con la alimentación
- falta de apetito; no tengo ganas de comer
- náusea vómitos
- estreñimiento diarrea
- llagas en la boca sequedad de boca
- los alimentos me saben raros
- o no me saben a nada
- problemas al tragiar los olores me desagradan
- me siento lleno/a enseguida
- dolor; ¿dónde?
- otros factores**

** como: depresión, problemas dentales, económicos
(sumar las puntuaciones correspondientes a cada uno de los síntomas indicados por el paciente)

Capacidad Funcional: en el curso del último mes calificaria mi actividad, en general, como:

normal y sin limitaciones

no totalmente normal, pero capaz de mantenerme activo y llevar a cabo actividades bastante normales

sin ganas de hacer la mayoría de las cosas, pero paso menos de la mitad del día en la cama o sentado/a

capaz de realizar pequeñas actividades y paso la mayor parte del día en la cama o sentado/a

encamado/a, raramente estoy fuera de la cama

(consignar como marcador final la condición de más alta puntuación)

Suma de las Puntuaciones: 1+2+3+4 = A

EL RESTO DE ESTE FORMULARIO SERÁ COMPLETADO POR SU MÉDICO. GRACIAS.

5. Enfermedad y su relación con los requerimientos nutricionales		(ver Tabla 2 en la hoja de instrucciones)
Diagnóstico principal (especificar) _____		
Estadio de la enfermedad (indicar el estadio si se conoce o el más próximo a él): I II III IV Otro: _____		
Edad _____ B		 B
6. Demanda Metabólica		 C
(ver Tabla 3 en las instrucciones)		
sin estrés metabólico		
estrés metabólico leve		
estrés metabólico moderado		
estrés metabólico elevado		
7. Evaluación física		 D
(ver Tabla 4 en las instrucciones)		
Puntuación Numérica Tabla 2 =		 B
Puntuación Numérica Tabla 3 =		 C
Puntuación Numérica Tabla 4 =		 D
8. Evaluación Global (VGS A, B o C)		
Bien nutrido		
Moderadamente ó sospechosamente mal nutrido		
Severamente mal nutrido		
(ver Tabla 5 en la hoja de instrucciones)		
Puntuación Numérica Total: A+B+C+D		(ver recomendaciones abajo)

Firma: _____ Fecha: _____

Recomendaciones Nutricionales

La valoración cuantitativa del estado nutricional del paciente sirve para definir en qué casos se recomienda intervención nutricional incluyendo: educación nutricional del paciente y familiares, manejo de síntomas, intervención farmacológica, e intervención nutricional apropiada. Una apropiada intervención nutricional requiere un apropiado manejo de los síntomas del paciente.

No requiere intervención nutricional en este momento. Volver a valorar durante el tratamiento.

2-3 Paciente y familiares requieren educación nutricional por parte de especialista en nutrición ó otro clínico, con intervención farmacológica según los síntomas (recuadro 3) y la analítica del paciente.

Requiere intervención de un especialista en nutrición junto con su médico/oncólogo según los síntomas indicados en el recuadro 3

9 Indica una necesidad crítica de mejorar el manejo de los síntomas del paciente y/o intervención nutricional / farmacológica".

FD Outrey, 2000.

INSTRUCCIONES: HOJA DE RECOGIDA DE DATOS Y TABLAS PARA LA CUANTIFICACIÓN DE LA ENCUESTA DE VALORACIÓN GLOBAL SUBJETIVA GENERADA POR EL PACIENTE (VGS-GP)

La valoración numérica final de la VGS-GP proviene de las puntuaciones totales obtenidas en los apartados A, B, C y D al dorso. Los recuadros 1-4 deben ser completados por el paciente. Las puntuaciones correspondientes a esos recuadros vienen indicadas entre paréntesis. La siguiente hoja sirve como ayuda para valorar cuantitativamente las diversas secciones de que consta la encuesta.

TABLA 1.—Cuantificación de la Pérdida de Peso

Sumando puntos se determinan la pérdida aguda y subaguda de peso. **Subaguda:** si se dispone de los datos de pérdida de peso durante el último mes, añadir los puntos obtenidos a los puntos correspondientes a la pérdida de peso aguda. Sólo incluir la pérdida de peso de 6 meses si no se dispone de la del último mes. **Aguda:** se refiere a los cambios de peso en las últimas dos semanas: añadir 1 punto al marcador de subaguda si el paciente ha perdido peso, no añadir puntos si el paciente ha ganado o mantenido su peso durante las 2 últimas semanas.

Pérdida Peso en 1 mes	Puntos	Pérdida de Peso en 6 meses
10% o superior	4	20% o superior
5 – 9,9%	3	10 – 19,9%
3 – 4,9%	2	6 – 9,9%
2 – 2,9%	2 – 5,9%	
0 – 1,9%	0	0 – 1,9%

Puntuación Total Recuadro 1 = Subaguda + Aguda = 1

TABLA 2.—Criterios de cuantificación de Enfermedad y/o Condiciones

La puntuación se obtiene adjudicando 1 punto a cada una de las condiciones indicadas abajo, que se correspondan con el diagnóstico del paciente:

Categoría	Puntuación
• Cáncer	1
• SIDA	1
• Caquexia Cardiaca o Pulmonar	1
• Úlcera por decubito, herida abierta o fistula	1
• Existencia de Trauma	1
• Edad superior a 65 años	1

Puntuación Total Tabla 2 = B

TABLA 3.—Cuantificación del Estrés Metabólico

La valoración del estrés metabólico se determina mediante una serie de variables conocidas cuya presencia produce un incremento de las necesidades calóricas y proteicas del individuo. Esta puntuación **es aditiva**, de forma que un paciente con fiebre superior a 39 °C (suma 3 puntos) y si está siendo tratado con 10 mg de prednisona de forma crónica (suma 2 puntos más), lo que hace un total de 5 puntos para el paciente en esta sección.

Estrés	Ninguno (0)	Leve (1)	Moderado (2)	Elevado (3)
Fiebre	sin fiebre	37 y < 38 °C	38 y < 39 °C	39 °C
Duración de la Fiebre	sin fiebre	<72 horas	72 horas	>72 horas
Esteroides	sin esteroides	dosis bajas (<10 mg prednisona o equivalente/día)	dosis moderadas (>10 y <30 mg prednisona o equivalente/día)	altas dosis de esteroides (30 mg prednisona o equivalente/día)

Puntuación Total Tabla 3 = B

TABLA 4.—Reconocimiento Físico

El reconocimiento físico del paciente incluye una evaluación subjetiva de tres aspectos de la composición corporal: tejido graso, masa muscular y estatus hidrático.

Ya que se trata de una valoración subjetiva, cada aspecto del examen es cuantificado por grado de deficiencia. Déficit musculares impactan más en la puntuación final que déficits de tejido graso. Definición de categorías: 0=sin déficit, 1+=déficit leve, 2+=déficit moderado, 3+=déficit severo. Las puntuaciones en estas categorías no son aditivas, pero son utilizadas para establecer clínicamente el grado de la deficiencia (ej.: presencia o ausencia de fluidos)

Tejido Graso:

Grasa en orbitales parpebrales	0	1+	2+	3+
Pliegue tricipital	0	1+	2+	3+
Acúmulos grasos en la cintura	0	1+	2+	3+
Déficit Graso Global	0	1+	2+	3+

Estatus Hídrico:

Edema de tobillo	0	1+	2+	3+
Edema de sacro	0	1+	2+	3+
Ascitis	0	1+	2+	3+
Estatus Hídrico Global	0	1+	2+	3+

Estatus Muscular:

Músculos temporales	0	1+	2+	3+
Clavículas (pectorales y deltoides)	0	1+	2+	3+
Hombros (deltoides)	0	1+	2+	3+
Músculos interóseos	0	1+	2+	3+
Escápula (latisimus dorsi, trapecio, deltoides)	0	1+	2+	3+
Quadriceps	0	1+	2+	3+
Gastronemios	0	1+	2+	3+
Estatus Muscular Global	0	1+	2+	3+

La evaluación cuantitativa global del estado físico del paciente se determina mediante una valoración global subjetiva de todos los déficits corporales que presente el paciente teniendo en cuenta que las deficiencias musculares pesan más que los déficit del tejido graso y éstos más que el exceso de fluidos.

Sin déficit	= 0 puntos
Déficit leve	= 1 punto
Déficit moderado	= 2 puntos
Déficit severo	= 3 puntos

Puntuación Total Tabla 4 = D

TABLA 5.—Valoración Global Subjetiva del Estado Nutricional del Paciente. Categorías

Categoría	Estado A	Estado B	Estado C
	Bien nutrido	Moderadamente malnutrido o sospechosamente malnutrido	Severamente malnutrido
Peso	Sin pérdida de peso o sin retención hídrica reciente	a. 5% pérdida de peso en el último mes (o 10% en 6 meses) Peso no estabilizado	a. >5% pérdida de peso en 1 mes (o >10% en 6 meses) peso sin estabilizar
Ingesta	Sin déficit o Mejora significativa reciente	Disminución significativa en la ingesta	Déficit severo en la ingesta
Impacto de la Nutrición en los Síntomas	Ninguno o Mejora significativa reciente permitiendo una ingesta adecuada	Existe Impacto de la Nutrición en los Síntomas (Sección 3 de la VGS-GP)	Existe Impacto de la Nutrición en los Síntomas (Sección 3 de la VGS-GP)
Funcionalidad	Sin afectación o Mejora reciente significativa	Deterioro Moderado o Deterioro reciente de la misma	Deterioro severo o Deterioro reciente significativo
Examen Físico	Sin déficit o Deficiencia crónica pero con reciente mejoría clínica	Evidencia de pérdida de leve a moderada de masa grasa y/o masa muscular y/o tono muscular a la palpación	Signos evidentes de malnutrición (ej.: pérdida severa de tejidos graso, muscular, posible edema)

* FD Ottery, 2000 Evaluación Global (A, B, o C) =

APPENDIX 5. EORTC QLQ C30 TEST

SPANISH (SPAIN)

EORTC QLQ-C30 (versión 3)

Estamos interesados en conocer algunas cosas sobre usted y su salud. Por favor, responda a todas las preguntas personalmente, rodeando con un círculo el número que mejor se aplique a su caso. No hay contestaciones "acertadas" o "desacertadas". La información que nos proporcione será estrictamente confidencial.

Por favor ponga sus iniciales:

Su fecha de nacimiento (día, mes, año):

31

Fecha de hoy (día, mes, año):

1. ¿Tiene alguna dificultad para hacer actividades que requieran un esfuerzo importante, como llevar una bolsa de compra pesada o una maleta?

En absoluto	Un poco	Bastante	Mucho
----------------	------------	----------	-------

1 2 3 4

2. ¿Tiene alguna dificultad para dar un paseo largo?

1 2 3 4

3. ¿Tiene alguna dificultad para dar un paseo corto fuera de casa?

1 2 3 4

4. ¿Tiene que permanecer en la cama o sentado/a en una silla durante el día?

1 2 3 4

5. ¿Necesita ayuda para comer, vestirse, asearse o ir al servicio?

1 2 3 4

Durante la semana pasada:

En absoluto	Un poco	Bastante	Mucho
----------------	------------	----------	-------

6. ¿Ha tenido algún impedimento para hacer su trabajo u otras actividades cotidianas?

1 2 3 4

7. ¿Ha tenido algún impedimento para realizar sus aficiones u otras actividades de ocio?

1 2 3 4

8. ¿Tuvo sensación de "falta de aire" o dificultad para respirar?

1 2 3 4

9. ¿Ha tenido dolor?

1 2 3 4

10. ¿Necesitó parar para descansar?

1 2 3 4

11. ¿Ha tenido dificultades para dormir?

1 2 3 4

12. ¿Se ha sentido débil?

1 2 3 4

13. ¿Le ha faltado el apetito?

1 2 3 4

14. ¿Ha tenido náuseas?

1 2 3 4

15. ¿Ha vomitado?

1 2 3 4

16. ¿Ha estado estreñido/a?

1 2 3 4

Por favor, continúe en la página siguiente

Durante la semana pasada:	En absoluto	Un poco	Bastante	Mucho
17. ¿Ha tenido diarrea?	1	2	3	4
18. ¿Estuvo cansado/a?	1	2	3	4
19. ¿Interfirió algún dolor en sus actividades diarias?	1	2	3	4
20. ¿Ha tenido dificultad en concentrarse en cosas como leer el periódico o ver la televisión?	1	2	3	4
21. ¿Se sintió nervioso/a?	1	2	3	4
22. ¿Se sintió preocupado/a?	1	2	3	4
23. ¿Se sintió irritable?	1	2	3	4
24. ¿Se sintió deprimido/a?	1	2	3	4
25. ¿Ha tenido dificultades para recordar cosas?	1	2	3	4
26. ¿Ha interferido su estado físico o el tratamiento médico en su vida familiar?	1	2	3	4
27. ¿Ha interferido su estado físico o el tratamiento médico en sus actividades sociales?	1	2	3	4
28. ¿Le han causado problemas económicos su estado físico o el tratamiento médico?	1	2	3	4

Por favor en las siguientes preguntas, ponga un círculo en el número del 1 al 7 que mejor se aplique a usted

29. ¿Cómo valoraría su salud general durante la semana pasada?

1 2 3 4 5 6 7

Pésima

Excelente

30. ¿Cómo valoraría su calidad de vida en general durante la semana pasada?

1 2 3 4 5 6 7

Pésima

Excelente

APPENDIX 6. GI.NET21 QLQ TEST

ENGLISH

EORTC QLQ – GLNET21

Patients sometimes report that they have the following symptoms or problems. Please indicate the extent to which you have experienced these symptoms or problems during the past week. Please answer by circling the number that best applies to you.

During the past week:

		Not at all	A little	Quite a bit	Very much
31.	Did you have hot flushes?	1	2	3	4
32.	Have you noticed or been told by others that you looked flushed/red?	1	2	3	4
33.	Did you have night sweats?	1	2	3	4
34.	Did you have abdominal discomfort?	1	2	3	4
35.	Did you have a bloated feeling in your abdomen?	1	2	3	4
36.	Have you had a problem with passing wind/gas/flatulence?	1	2	3	4
37.	Have you had acid indigestion or heartburn?	1	2	3	4
38.	Have you had difficulties with eating?	1	2	3	4
39.	Have you had side-effects from your treatment? (If you are not on treatment please circle N/A)	N/A	1	2	3
40.	Have you had a problem from repeated injections? (If not having injections please circle N/A)	N/A	1	2	3
41.	Were you worried about the tumour recurring in other areas of the body?	1	2	3	4
42.	Were you concerned about disruption of home life?	1	2	3	4
43.	Have you worried about your health in the future?	1	2	3	4
44.	How distressing has your illness or treatment been to those close to you?	1	2	3	4
45.	Has weight loss been a problem for you?	1	2	3	4
46.	Has weight gain been a problem for you?	1	2	3	4
47.	Did you worry about the results of your tests? (If you have not had tests please circle N/A)	N/A	1	2	3
48.	Have you had aches or pains in your muscles or bones?	1	2	3	4
49.	Did you have any limitations in your ability to travel?	1	2	3	4

During the past four weeks:

50.	Have you had problems receiving adequate information about your disease and treatment?	1	2	3	4
51.	Has the disease or treatment affected your sex life (for the worse)? (If not applicable please circle N/A)	N/A	1	2	3

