Both the tumor itself (functionality or location) and the treatments used (surgeries and systemic treatments) can have a direct impact on the nutritional status of the patient. Nutritional status plays a very important role in those patients with functioning GEP NETs, since nutrition is very affected due to the excessive production of gastrointestinal hormones, peptides and amines that can lead to malabsorption, diarrhea, steatorrhea or alterations in intestinal motility. In the case of carcinoid syndrome, serious nutritional deficits can also occur because hormonal secretion leads to an increase in the production of serotonin and, as consequence, to a deficit of niacin. Besides, surgical management of NETs, that involves resection and / or alteration of the anatomy of the gastrointestinal tract, or the treatment with SSA, which suppresses the secretion of pancreatic enzymes as well as the secretion and functioning of gastrointestinal hormones, can condition secretory, motor or malabsorptive alterations with relevant consequences at the nutritional level such as fat malabsorption or fat-soluble vitamin deficiencies. Systemic drugs such as chemotherapy, interferon, mTOR inhibitors or vascular endothelial growth factor (VEGF) inhibitors also have deleterious effects on nutritional status as they cause anorexia, weight loss, diarrhea and alterations of the hepatic function.

Therefore, disease-related malnutrition (DRM) in patients with NETs is multifactorial [1]

and its importance relies in the clinical repercussions it has on the patient: it worsens quality of life, decreases response to treatment and increases the complications, the need for hospitalization, the hospital stay, the costs and mortality. Diverse studies have shown that poor nutritional status in patients with pancreatic NETs can negatively influence patient survival and can even predict tumor response in patients who receive chemoembolization as a treatment for liver metastases [2-5]. Another study published in 2018 demonstrated a novel association between nutritional status and GEP-NET aggressiveness in a selected cohort of adult patients, in part due to their adherence to the Mediterranean diet [6]. The study concluded that the dietary pattern of the Mediterranean diet could be beneficial for GEP-NET patients and could modulate the risk of tumor aggressiveness, offering a practical strategy for the treatment of these patients [6].

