8. HYPOTHESIS AND OBJECTIVES

Malnutrition in GEP NET patients entails greater morbidity and mortality and has been described as frequent. However, the prevalence of malnutrition or risk of malnutrition in patients with GEP NET in our country is unknown and its diagnosis is probably underestimated. Knowledge on this subject is still scarce and this is where the motivation for this observational study has arisen from.

NUTRIGETNE aims to be the first stage to subsequently allow to carry out nutritional intervention studies in NET patients. The study will make an extensive description of the impact of the nutritional status in patients with NET. The results will allow us to advance in the knowledge about different nutritional problems that appear in patients with NET, in the use of screening tools in these patients and in relevant information for future clinical practice guidelines.

There are 3 main hypothesis:

1. Malnutrition and the risk of malnutrition in patients with GEP NET is frequent, but its prevalence in our environment is unknown.
2. The nutritional status may influence the prognosis, survival, quality of life or response to treatments in GEP NET patients.
3. Therapeutic approaches in GEP NET patients could have a direct impact on the nutritional status of these patients and may be a possible benefit on early intervention in the event that this negative impact exists.

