8.2. Secondary Objectives

- Describe the nutritional status of NET patients by using clinical malnutrition scores, anthropometry, bioimpedanciometry, and analytical parameters.
- Describe the nutritional status of NET patients according to the type of NET.
- Study the association between the nutritional status and the quality of life of the patients.
- Study the association between the nutritional status and the stage of the disease and tumor grade.
- Study the association between the nutritional status and the treatments received by the patient.

- Study the association between the nutritional status and the hormonal functionality of the tumor.
- Study the association between nutritional status and survival of NET patients.
- Describe specific deficiencies or deficiencies of vitamins or trace elements in these patients and study if there is a correlation of these with the treatments or tumor types.

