9.5. Endpoints

- Demographic characteristics: Age and ECOG at inclusion, sex, complete physical examination (including blood pressure and heart rate), enolic and smoking habits, other cancer history.
- NET diagnosis: date of initial diagnose, age at diagnose.
- NET at baseline: location of primary tumor, histological grade, TNM grade, Ki-67, mitotic index, metastatic locations, functional status of the tumor.
- NET treatment:
 - a. Prior treatments: systemic therapies for NET (type, start and end date, best response, progression date), locoregional therapies (type, start and end date, best response, progression date), surgery (dates, outcome) and radiotherapy (type, dose, start and end date).
 - b. Current treatments (at baseline): systemic therapies for NET (type, start date, best response), locoregional therapies (type, start date, best response) and radiotherapy (type, dose, start date).
 - c. Hospitalizations (at baseline): cause, start and end date.
- Target nutritional history: regular weight, loss of weight (start date, duration), weekly food intake (calculation of mean daily caloric intake, mean protein intake, (animal and vegetal), mean carbohydrates intake (simple or complex), mean fat intake (saturate, monounsaturated, polyunsaturated, n-3 and n-6), and mean fiber intake (soluble and insoluble). The PREDIMED score test will be used (appendix 2). Calculation of caloric-protein nutritional requirements, according to ESPEN guidelines. Need for supplementation, if necessary, type of oral nutritional supplement (ONS) used, volume administered (ml / day), type of administration regimen (continuous or discontinuous). Number of intakes per day and volume of intakes and existence of intolerance related to enteral nutrition (EN): Diarrhea, constipation, bloating, nausea, vomiting, regurgitation, fever, ...).
- Nutritional screening test: NRS test (nutritional risk screening) (appendix 3) and SGA test (subjective global assessment) (appendix 4). The GLIM criteria for diagnosis and stratification of malnutrition will be applied.

- Quality of life (QoL) test: EORTC QLQ-C30 (European Organisation for Research and Treatment of Cancer Quality of Life Questionnaire)(appendix 5) and the NET specific questionnaire (GI.NET21)(appendix 6).
- Anthropometry: height, weight at baseline, BMI, triceps fold, brachial circumference, abdominal circumference, calf circumference.

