9.8. Data analysis

The study will be analyzed descriptively, using descriptive epidemiological methods as detailed below. All results, including p-values and confidence intervals, are to be interpreted descriptively only.

- The analyses will be performed to the total population included fulfilling all selection criteria.

Additional subgroup analyses may be performed to fulfill secondary objectives (depending on the finally observed number of patients in such subgroups), including but not limited to: Tumor type, stage, grade and functionality, treatment type or survival.

The data will be summarized using the mean (standard deviation) and the median (1st and 3rd quartiles) in the case of continuous variables and using relative and absolute frequencies in the case of categorical variables. The prevalence together with its corresponding 95% confidence interval will be estimated by fitting a binomial model. The associations between the nutritional status and the quality of life of the patients, the stage of the disease and the tumor grade will be contrasted using ordinal regression models. Survival will be analyzed using cox regression models or parametric survival models according to the assumptions that meet the data. All analyzes will be performed using R software (version 4.03 or higher).

The final analysis will be performed within 6 months after the inclusion of the last patient. The final data interpretation and presentation in reports, scientific publications and/or congresses will be done within 12 months after the final analysis. The final report will be presented to the competent authorities 12 months after the end of study.

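### The planned nutrition and quality-of-life regression names no covariate, so its crude odds ratio can partly reflect tumour functionality, which is already collected and could be adjusted for

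*Combined protocol and SAP*

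**What the plan says.** **The objective and its hypothesis.** Section 8.2 lists as a secondary objective: "Study the association between the nutritional status and the quality of life of the patients". The second hypothesis in section 8 gives this a direction: "The nutritional status may influence the prognosis, survival, quality of life or response to treatments in GEP NET patients".

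**The model.** Section 9.8 says that the associations of nutritional status with "quality of life of the patients, the stage of the disease and the tumor grade will be contrasted using ordinal regression models". The synopsis repeats the sentence. It names no covariate and no quality-of-life scale or item. It does not say which variable is the outcome.

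**Hormones and nutrition.** Section 7 says that in functioning tumours "nutrition is very affected due to the excessive production of gastrointestinal hormones, peptides and amines that can lead to malabsorption, diarrhea, steatorrhea". It adds that carcinoid syndrome can bring serious deficits.

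**The questionnaires.** QLQ-C30 item 17 (Appendix 5) asks about diarrhoea. GI.NET21 items 31 to 33 (Appendix 6) ask about hot flushes, looking flushed ("Have you noticed or been told by others that you looked flushed/red") and night sweats.

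**Functional status.** Section 9.5 collects "functional status of the tumor" at baseline. Section 8.2 gives it a separate objective against nutrition. Section 9.8 lists functionality among subgroup analyses that are optional and depend on patient numbers. Section 9.8 also says that all results are to be read descriptively, and section 10.6 warns in general terms about causal interpretation.

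**The concern.** By the protocol's own account, hormone secretion lies upstream of nutritional status and of at least one quality-of-life symptom, diarrhoea. A variable that worsens both produces an association between them even if nutrition has no effect on quality of life. This applies whichever of the two is made the outcome. The study is cross-sectional, so timing cannot separate the explanations afterwards.

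Adjusting for functional status would not remove a genuine path from nutrition to quality of life, because functionality comes before nutrition on the protocol's account. Items 31 to 33 do not appear on the NRS or SGA forms, so dropping questions shared between instruments would not help either.

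What is at stake is how the result on the second hypothesis is read. Section 8 presents the study as a first step towards nutritional intervention studies. A crude odds ratio that mixes nutrition with tumour functionality would be a weaker basis for that step than it looks.

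**Working it through.** **The plan's own figure.** None is given for this model. The only design figure is 400 patients for an interval of plus or minus 3 points at 30% prevalence (section 9.3). At 95% confidence, 1.96² × 0.30 × 0.70 / 0.03² gives 897, and 400 patients give 1.96 × √(0.21/400) = 4.5 points. That mismatch is a separate matter. Here 400 is used only as the planned enrolment.

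**Inputs from the documents.** N = 400 and malnutrition 30% (section 9.3); a four-level item (Appendices 5 and 6); ordinal regression (section 9.8).

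**Assumed, because the documents are silent.** Functioning share 20% or 40%; odds ratio of functionality with malnutrition 1.5 to 3; odds ratio of functionality with the item 2 to 8; 50% of non-functioning patients report the symptom at any level.

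**Models.** With M = malnutrition and F = functioning tumour, malnutrition follows logit P(M=1) = b₀ + log(OR_FM)·F, with b₀ set so that 30% are malnourished overall. The item depends on F only, so the true nutrition odds ratio is 1. The crude fit is logit P(Y≥k) = α_k + β·M; the adjusted fit adds γ·F.

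**Hand check, split at any symptom.** Functioning patients are over-represented among the malnourished.
- Weak (share 20%, odds ratios 1.5 and 2): malnutrition 37% v 28%. P(F|M) = 0.2×0.37/0.30 = 0.247; P(F|not M) = 0.2×0.63/0.70 = 0.18. Symptom 0.667 in functioning, 0.50 otherwise. Malnourished 0.541, others 0.530; odds ratio 1.179/1.128 = 1.05.
- Middle (40%, 2 and 4): malnutrition 39% v 24%. P(F|M) = 0.520; P(F|not M) = 0.349. Symptom 0.80 v 0.50. Malnourished 0.656, others 0.605; odds ratio 1.907/1.529 = 1.25.
- Strong (40%, 3 and 8): malnutrition 44% v 21%. P(F|M) = 0.587; P(F|not M) = 0.32. Symptom 0.889 v 0.50. Malnourished 0.728, others 0.624; odds ratio 2.68/1.66 = 1.61.

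**Simulation of the full four-level model, 200 runs per scenario.** The last two columns have functional status added.

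| Share | OR with malnutrition | OR with item | Crude OR | Crude p<0.05 | Adjusted OR | Adjusted p<0.05 |
|---|---|---|---|---|---|---|
| 20% | 1.5 | 2 | 1.03 | 6% | 0.99 | 3% |
| 20% | 2 | 4 | 1.18 | 12% | 1.00 | 6% |
| 40% | 2 | 4 | 1.26 | 27% | 1.01 | 7% |
| 40% | 3 | 4 | 1.42 | 40% | 1.00 | 5% |
| 40% | 3 | 8 | 1.66 | 73% | 1.01 | 4% |
| 30% | 1 (no link) | 4 | 1.02 | 4% | 1.03 | 6% |

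Over the 18 linked scenarios the crude odds ratio was 1.03 to 1.66 and the adjusted one 0.97 to 1.02. Adjusted rejection was 3% to 9%, broadly consistent with 5% given a simulation error of √(0.05×0.95/200) = 1.5 points.

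**If the outcome is a total score.** Simulations with a 21-item total, in which functionality affects only items 31 to 33, gave crude odds ratios of about 1.03 to 1.11, with 4% to 10% nominally significant. They also rest on an assumed correlation between items, so they indicate dilution and not an exact size.

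**The case against.** The other side has real force.

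- **Descriptive purpose.** Section 9.8 says that results are descriptive, the objective speaks of association, and section 10.6 warns about causality. A crude association is a legitimate descriptive quantity. This limits the point, but it does not change what the odds ratio contains once it is set against a hypothesis about influence.
- **The symptom link.** A reader might infer that items 31 to 33 measure a functioning tumour directly. The documents do not say so: section 7 mentions neither flushing nor sweating. Section 7 also attributes diarrhoea to chemotherapy, interferon, and mTOR and VEGF inhibitors. All patients are on active treatment (section 9.2.1), and section 7 says that somatostatin analogues, usually the first line, keep hormone excess in check. The contrasts may therefore be weaker than assumed. This stands.
- **Size.** The larger figures need a single symptom item as outcome and strong links, and the plan does not say that items will be analysed singly. This stands too, and the range has to include values near 1.
- **One covariate among several.** Section 7 also links surgery, somatostatin analogues and systemic drugs to nutrition. The adjusted value near 1.0 is built into the simulation, where functionality is the only confounder. It shows that this one source is removed, not that the adjusted estimate is free of confounding.
- **Optional subgroup.** Functionality is on the list, but an analysis left to discretion and patient numbers is not a planned adjustment.

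**Conclusion.** The point holds in a limited form. The plan fits no named covariate, the protocol itself describes functionality as a cause of poor nutrition and of diarrhoea, and the variable is on the data form. The crude association can therefore partly reflect functionality.

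How much is unknown. Under the stated assumptions the spurious odds ratio is about 1.03 with weak links, or with a total score in which only items 31 to 33 are affected. It reaches about 1.4 or more for one symptom item with strong links, and 1.66 at the extreme tried. If functionality were unrelated to malnutrition there would be no bias.

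A reader might infer that the reported association would be mainly spurious, or that the study claims nutritional support could relieve tumour symptoms. The documents support neither: they give no link strengths, and they do not rest intervention on this association. It is a secondary objective, and the primary prevalence estimate is unaffected.

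**What to change.** In section 9.8 and the synopsis:

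1. Add tumour functional status (functioning, non-functioning, unknown), from section 9.5, as a covariate in the ordinal models of nutrition and quality of life. Report the adjusted odds ratio beside the crude one.
2. If QLQ-C30 item 17 or GI.NET21 items 31 to 33 are analysed as items or symptom scales, also show the association separately in functioning and non-functioning patients.
3. State that this adjustment does not remove confounding by treatment or surgery, which section 7 also links to nutrition, and that a simple functioning/non-functioning split may leave some residual confounding.

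The cost is analysis wording, one or two degrees of freedom and a small loss of precision. No new data are needed, and the crude result is kept.
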